c. Inclusion Criteria for participation in follow-up study with Dotatate

- Initial dotatate PET scan consistent with active sarcoidosis. Defined as focally increased radiotracer activity in at least one left ventricular wall.

- Being on corticosteroid therapy at a dose of ≥ 10 mg/day of oral prednisone or equivalent for at least 6 weeks since initial dotatate PET scan.

IV. SUBJECT ENROLLMENT

Recruitment Procedures: Potential subjects will be recruited from the following sources: 1) Cardiomyopathy clinic; (2) Sarcoidosis clinic and 2) Nuclear Cardiology Laboratory.

Screening procedures will include daily or weekly queries for potential eligible subjects from lists of patients who have either undergone nuclear imaging or are scheduled to undergo imaging procedures for sarcoidosis. [name] will plan on educating the Nuclear Medicine Department staff about the study (recruitment information) as an additional way to ensure potential eligible patients are referred to the study. Our Nuclear Medicine Department staff will be instructed to notify [name] if they encounter an abnormal FDG-PET suggestive of active cardiac sarcoidosis, so that the study can be introduced by the nuclear technologists, physiologists or physicians before they leave the Nuclear Medicine facility.

If potential candidate is identified in the sarcoidosis clinic and/or cardiomyopathy clinic, patient's doctor or clinic staff will introduce the study to the patient. If patient is interested in learning more about the study, [name] will be notified, who will further discuss the study with the patient after the conclusion of his/her appointment with patient's doctor.

If potential patient is identified in the Nuclear Cardiology Laboratory the day of the patient's FDG PET scan, patient will be approached by one of the nuclear technologists, physiologists or physicians before they leave the Nuclear Medicine facility. Only non-study staff members may approach a potential patient in this manner. They can determine whether or not a patient may be interested in finding out more information and can refer him or her to the study team as appropriate. In this setting, the patient may be an inpatient or outpatient.

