DOTATATE will be given intravenously at the dose of 4.0 mCi (148 MBq). They will then be observed for 60 minutes post DOTATATE injection at the nuclear medicine lab.

Cardiac acquisition: Individuals will be positioned with the help of a CT topogram (grid over the heart, level of the carina), and a low-dose CT scan (120 kVp, 20 - 30 mA) will be acquired for attenuation correction of PET emission data to cover the entire chest. This will be followed by a 20-minute ECG-gated 3-D PET acquisition of the chest and myocardium.

Imaging Processing:

All PET images will be reconstructed with attenuation correction (Matrix 128x128, OSEM, subsets 28, iteration 2, post filter 6.0 mm), and processed and reviewed using the vendor-supplied HERMES software package.

d. Data to be collected and when the data is to be collected

Visit 1. We will collect demographics data, medical history, prior treatments, and concomitant medications, as well as confirm a negative STAT quantitative serum hCG testing prior to the administration of Octreoscan or DOTATATE.

After visit 3 for OctreoScan or after visit 2 for DOTATATE we will analyze and interpret the images as following:

Image Interpretation for OctreoScan:

OctreoScan uptake in the heart will be assessed both qualitative and semi-quantitatively.

1. Qualitative Assessment of OctreoScan cardiac uptake: Two board-certified nuclear medicine physicians will review the early and delayed whole body planar and SPECT/CT images independently of each other and grade each image set based on OctreoScan uptake in the heart as: 1) negative, 2) borderline positive or 3) definitely positive. In this latter case, the number and location (relative to the left ventricular wall position) of positive lesions will be recorded. Similarly, FDG-PET studies (performed as part of the inclusion criteria) will be reviewed and the number and location of FDG-avid lesions recorded.

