2. Semi-quantitative assessment of OctreoScan cardiac uptake: A heart to blood pool background ratio will be calculated using a circular region of interests (ROI) applied to each focus of increased radiotracer uptake visualized in the left ventricle on the transverse and/or coronal tomographic slice of the fused SPECT/CT images. A background ROI of the same size will be applied to the blood pool in the left ventricular cavity. In addition, the relative myocardial contrast will be assessed with measurement of myocardial uptake in ROIs positioned in: 1) interventricular septum 2) lateral wall 3) anterior wall and 4) inferior wall. ROI placement will be confirmed via image fusion with the CT portion from the SPECT/CT study (similar to Figure 2). This qualitative and semiquantitative approach will be performed in both early and delayed datasets by 2 separate nuclear medicine physicians.

Image Interpretation for DOTATATE:

DOTATATE uptake in the heart will be assessed both qualitative and semi-quantitatively.

1. Qualitative Assessment of OctreoScan cardiac uptake: Two board-certified nuclear medicine physicians will review the limited whole body and cardiac PET/CT images independently of each other and grade each image set based on DOTATATE uptake in the heart as: 1) negative, 2) borderline positive or 3) definitely positive. In this latter case, the number and location (relative to the left ventricular wall position) of positive lesions will be recorded.

2. Quantitative assessment of DOTATATE cardiac uptake: The axial PET image slice with maximum cardiac uptake will be selected. A standardized 15 mm circular region will be placed over each myocardial wall area with the peak activity. ROI placement will be confirmed via image fusion with the CT portion from the PET/CT study. Each ROI will be used to derive maximum (SUVmax) and mean standardized uptake values (SUVmean). A background ROI of the same size will be applied to the blood pool in the left ventricular cavity, and similarly, SUVmax and SUVmean will be derived to serve as reference. Then, signal-to-background ratios will be calculated.

This qualitative and semi-quantitative approach will be performed in both early and delayed datasets by 2 separate nuclear medicine physicians.

BIOSTATISTICAL ANALYSIS

a. Specific data variables being collected for the study

Please see excel attachments

b. Study endpoints

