Primary Endpoint: Positive or abnormal OctreoScan or DOTATATE uptake in patients with cardiac sarcoidosis

Secondary Endpoint: Differences in OctreoScan uptake at 4 hours vs. 24 hours post-radiotracer injection

c. Statistical methods

Data Ascertainment and Analysis:

All statistical analysis will be done using SPSS (version 21.0). A P value <0.05 will be considered statistically significant for all calculations.

Qualitative assessment of OctreoScan or DOTATATE cardiac uptake: First, Cohen's kappa coefficient will be used to examine the visual inter-rater agreement between readers. We expect a kappa of at least 0.9 (excellent). Subsequently, the percentage of patients with abnormal OctreoScan or DOTATATE will be compared between patients with suspected sarcoidosis and those in a control group (Table 1, Figure 2) using chi2.

Semiquantitative assessment of OctreoScan or DOTATATE cardiac uptake: The heart-to-blood pool ratio is a unitless continuous variable. We will use paired t-test to compare within group OctreoScan uptake between early and delayed imaging, and independent-measures t test to compare OctreoScan or DOTATATE uptake between patients with suspected sarcoidosis and the control group.

We will also investigate whether delayed imaging may lead to improved lesion detection performance due to a higher/better target-to-background ratio compared to early imaging. We will employ chi2 to compare if percentage of patients with abnormal OctreoScan varies significantly both on a patient- and lesion-basis between early and delayed imaging in both study groups.

Evaluation of early vs. delay imaging: We will employ chi2 to compare if percentage of patients with abnormal OctreoScan varies significantly both on a patient- as well as lesion-basis between early and delayed imaging in both study groups.

Comparison with FDG-PET: We will also compare if foci of increased OctreoScan or DOTATATE uptake are similar in number and localization compared to FDG-PET scans.

Expected Results:

Our main hypothesis is that OctreoScan or DOTATATE uptake in the heart will be semiquantitatively (heart-to blood pool ratio will be ≥ 2.0) high enough to allow visualization of OctreoScan or DOTATATE activity in patients with cardiac sarcoidosis, compared to the control group, where myocardial uptake will be similar to blood pool activity (heart-to blood pool ratio of ~ 1.0).

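### Tracer foci are recorded only on definitely positive scans while FDG foci carry no grade condition, so borderline scans add no visually recorded foci to the lesion comparisons

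*Combined protocol and SAP*

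**What the plan says.** Section V.d, Image Interpretation for OctreoScan, item 1, asks two independent readers to "grade each image set based on OctreoScan uptake in the heart as: 1) negative, 2) borderline positive or 3) definitely positive". The next sentence limits what is written down: "In this latter case, the number and location (relative to the left ventricular wall position) of positive lesions will be recorded". The DOTATATE part uses the same scale ("grade each image set based on DOTATATE uptake in the heart as: 1) negative, 2) borderline positive or 3) definitely positive") and repeats the limiting sentence.

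The FDG scans that qualified the patient are also to be reviewed, and "the number and location of FDG-avid lesions recorded". No grade is attached to that step.

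The semi-quantitative steps carry no grade condition. For OctreoScan a region of interest is "applied to each focus of increased radiotracer uptake visualized in the left ventricle", and each of the four walls is measured as well. For DOTATATE the slice with the highest cardiac uptake is chosen, and "A standardized 15 mm circular region will be placed over each myocardial wall area with the peak activity".

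Two sets of analyses use these reads. Sub-Aim 2 and the FDG paragraph of the Statistical methods compare the number and location of foci between tracer and FDG. The early-versus-delayed paragraph compares 4 h with 24 h OctreoScan by patient and by lesion. The primary endpoint is "Positive or abnormal OctreoScan or DOTATATE uptake in patients with cardiac sarcoidosis", analysed as a percentage of abnormal scans.

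**The concern.** Two modalities are to be compared on how many foci they show and where, but they are not recorded under the same condition. A tracer focus reaches the visual record only if the whole scan is graded definitely positive. An FDG focus reaches it regardless. The difference in counts then partly reflects the recording rule, and the plan does not say how a borderline scan is handled in the comparison.

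The same gate affects the early-versus-delayed comparison differently. It applies equally at both times, but it acts on the scan and not on the focus, so a change in the scan's grade can make an already visible focus appear for the first time at 24 h.

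A related gap is that nothing maps the middle grade to abnormal or not abnormal in the primary percentage. If that is settled after the reads, the estimate can be chosen with the data in view.

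Foci that are never written down can be recovered only by reading the scans again, so this is best settled before the reads.

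**Working it through.** The plan contains no figure that depends on the borderline rule, so there is nothing to reproduce. The check sets the recording rules side by side and then gives a sense of scale under stated assumptions.

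**1. Recording rules (section V.d)**

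| Read | Graded? | Number and location recorded when |
|---|---|---|
| OctreoScan, 4 h and 24 h | three levels | definitely positive only |
| DOTATATE | three levels | definitely positive only |
| FDG | no grade stated | no condition stated |

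The FDG sentence opens with a word of similarity, but that cannot import the condition, because no FDG grade is defined. Section III.a also requires abnormal myocardial FDG uptake for entry, so FDG foci are to be expected in every patient.

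**2. Effect on the FDG count**

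Inputs from the plan: N = 30 (10 OctreoScan + 20 DOTATATE, section V.a). Assumptions: 18 definite, 6 borderline and 6 negative scans; 2 FDG foci per patient; 2 tracer foci per definite scan; 1 or 2 per borderline scan.

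- FDG foci: 30 × 2 = 60. Tracer foci visually recorded under the rule: 18 × 2 = 36.
- Borderline scans entered as zero: 36/60 = 60%.
- Borderline patients excluded from both counts: FDG foci 24 × 2 = 48, and 36/48 = 75%.
- Borderline foci recorded: (36 + 6 × 1)/60 = 42/60 = 70%, or (36 + 6 × 2)/60 = 48/60 = 80%.

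The same images give 60% to 80%, depending on a rule that the plan leaves open.

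**3. Effect on 4 h versus 24 h**

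Take one patient with two foci visible at both times. The scan is graded borderline at 4 h and definitely positive at 24 h because one focus has become more intense. Foci recorded: 0 at 4 h and, if the reader lists both, 2 at 24 h. Both look new, although neither is.

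**4. Effect on the primary percentage**

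With B borderline scans of N, the two possible rules differ by B/N. For N = 30:

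- B = 3: 10 points. B = 6: 20 points. B = 9: 30 points.
- With 18 definite and 6 borderline (Clopper-Pearson 95% intervals): borderline as not abnormal, 18/30 = 60.0% (40.6 to 77.3); as abnormal, 24/30 = 80.0% (61.4 to 92.3); excluded, 18/24 = 75.0% (53.3 to 90.2).

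**5. Effect on the test against controls**

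The 15 controls of section I.c were not graded on this scale in the text. I assume 0/15 abnormal, since their myocardium could not be told visually from blood pool. The fewest abnormal patients of 30 that give p < 0.05 are:

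- Pearson chi-square: 7 (p = 0.042)
- Fisher exact: 8 (p = 0.038)
- Continuity-corrected chi-square: 9 (p = 0.048)

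With 9 or more definite scans the result is therefore significant whichever side borderline falls on. The rule can decide the result only when few scans are definite. For example, 2 definite and 2 borderline of 10 OctreoScan patients give Pearson p = 0.071 (2/10) or p = 0.0075 (4/10).

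**The case against.** Several points on the other side are sound.

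- **Focus data may exist elsewhere.** The OctreoScan ratio step covers every visualised focus whatever the grade, and the wall measurements are ungraded for both tracers. It would be wrong to infer that borderline foci are discarded altogether. But the plan does not link these measurements to the lesion comparisons, and the DOTATATE step works from one selected slice, so it is not a list of foci. The data-variable list is in attachments not shown and may hold more; it would not remove the written restriction.
- **No rule sets borderline scans to zero.** A reader might infer that they count as zero lesions, or that the matching FDG foci become FDG-only by rule. The text says neither. Zero, missing and excluded are all open.
- **4 h and 24 h share one rule.** A reader might infer unequal counting between the two times. That is not so, and a real gain in conspicuity is what the delayed scan is meant to show. What stands is narrower: the whole-scan gate cannot separate a focus that became clearer from one that was not there before.
- **A strict threshold is defensible.** Section I.c attributes higher inferior-wall and septal ratios in controls to scatter from liver and spleen. Weak foci there may be artefact, and adding them could worsen agreement on location. The tilt is therefore clear for the count but not for location.
- **Section III.c is not a rival endpoint definition.** Its wording, "Defined as focally increased radiotracer activity in at least one left ventricular wall", governs entry to the follow-up scan only.

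**Conclusion.** The recording rule needs changing. It is stated in the text for both tracers, it has no counterpart for FDG, and it feeds a comparison of number and location. Its direction is towards fewer tracer foci in the count. Its size cannot be derived from the documents, because neither the borderline frequency nor the number of foci per scan is given. With 6 of 30 scans borderline and two FDG foci per patient, the recorded tracer-to-FDG ratio is 60% with borderline scans as zero, 75% with them excluded, and 70% or 80% with their foci recorded.

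The unassigned borderline grade in the primary percentage is a supporting point, mostly one of missing detail. It moves the estimate by 10 points for each 10% of scans graded borderline. A reader might infer that it puts the significance test in doubt. Under the assumption of 0/15 abnormal controls, that is so only when few scans are definite.

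**What to change.** In section V.d, for OctreoScan and DOTATATE alike, record the number, wall and confidence (borderline or definite) of every focus on scans of grade 2 and grade 3. Record FDG foci with the same confidence label.

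In the Statistical methods, run the FDG comparison and the lesion-based 4 h versus 24 h comparison on definite foci and again on definite plus borderline foci. State that a borderline scan enters with its recorded foci and is not treated as zero or missing.

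Before the reads, state whether borderline counts as abnormal in the primary percentage, and report the other choice as a sensitivity analysis. Either choice is workable; what matters is that it is fixed in advance.

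The cost is extra fields on the reading form and one extra analysis row, with no added scans. The confidence label keeps weak foci, including possible scatter in the inferior wall and septum, apart from definite ones. None of this needs a consensus or adjudication read, which the plan does not provide for.

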patients (7 men and 8 women, mean age 62 years) who underwent OctreoScan with SPECT/CT of the chest for a clinical indication between the periods of April and November of 2013 at the University of Washington in Seattle. Most common clinical indication was detection of local and/or metastatic neuroendocrine tumors. Patients were injected with ~ 6 mCi of OctreoScan, and SPECT/CT of the chest was acquired 24 hr post-injection. OctreoScan uptake was semiquantitatively calculated using a target to blood pool ratio approach. Figure 2 depicts fused SPECT/CT images of how this was performed. Circular region of interests (ROI) of ~20 mm diameter were applied to left ventricular (LV) cavity blood pool (used as background, 2A and 2D), LV anterior (2B), inferior (2C), lateral wall (2E) and septum (2F), as well as the lungs (not shown), liver (2G), spleen (2G) and kidneys (2H). Results: Visually, the myocardium exhibited indistinguishable activity compared to the LV blood pool. However, there was significant LV regional differences in the uptake ratio/index as shown in **Table 1**. The inferior wall and septum showed higher (above blood pool) and the lateral and anterior walls lower (below blood pool) uptake ratios. This is most likely due to scatter emitted from the liver and spleen (Fig 2G) into the inferior wall (Fig 2C) and, to a lesser extent, the inferior portion of the septum. Likewise, identification of the septal wall (Fig 2F) was difficult given the lack of enough contrast definition on SPECT and CT images, for which an anatomical assumption was made, which makes ROI-based estimates less accurate at this location. These data demonstrated that under baseline conditions. OctreoScan uptake in the heart is indistinguishable from LV blood pool (~ 0.94 ± 0.17). These findings provide solid empirical basis for the work proposed in this project; the hypotheses are mechanistically plausible, clinically important, and testable.

d. Differences between OctreoScan and DOTATATE

There are important biological, technical, and practical differences between these radiopharmaceuticals that deserve a brief mention. Like indium-111 pentetrotide (Octreoscan®), 68-gallium dotatate has similar affinity for the same group of somatostatin receptors in inflammatory leukocytes (preferentially somatostatin receptor 2). The availability of 68-gallium dotatate provides several advantages, which are highly beneficial to the patients in this pilot study, including:

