- a. higher contrast and spatial resolution of PET/CT for detection of small lesions, which we think will result in improved sensitivity as compared to indium-111 pentetrotide SPECT;
- b. a nearly 75% reduction in the whole body effective radiation dose to patients from a single administration of gallium-68 dotatate (from 16.4 mSv for Octreoscan to 4.3 with Dotatate);
- c. convenience for patients and practical to perform. The entire gallium-68 dotatate PET imaging procedure takes ~2 hours in a single visit, compared to ~24 hours over 2 visits for octreoscan imaging.

II. SPECIFIC AIMS

Aim 1

To investigate if patients with clinically suspected cardiac sarcoidosis exhibit a myocardial OctreoScan or DOTATATE signal high enough (heart-to-blood pool ratio ≥ 2.0) to be visually detected compared to a control group of individuals (expected heart-to-blood pool ratio of ~ 1.0).

Sub-Aim1

To evaluate whether 4-hour (early) compared to 24-hour (delayed) post-OctreoScan injection imaging yields similar lesion detection performance.

Sub-Aim2

To correlate localization and number of increased radiotracer foci between FDG-PET and OctreoScan or between FDG-PET and DOTATATE studies.

Sub-Aim3

To explore the effect of treatment on DOTATATE activity in the heart on follow-up scans

III. SUBJECT SELECTION

We will enroll 30 adult subjects meeting the following inclusion/exclusion criteria.

a. Inclusion Criteria for initial study

- Individuals aged 18 or older

- Documentation of biopsy-proven sarcoidosis OR patients with typical findings on FDG PET and MRI without previous biopsy.

- Clinical suspicion of cardiac involvement defined as the presence of any of the following: high-degree A-V nodal block, complete bundle branch block, reduced left or right ventricular systolic function, any cardiac arrhythmia, and/or unexplained chest pain, dyspnea or syncope

- PET/CT imaging demonstrating abnormal myocardial FDG uptake consistent with active inflammatory myocardium.

b. Exclusion Criteria for initial study

-Initiation of steroids or any other immunosuppressive medication(s) following the completion of FDG-PET, as these medications, in theory, may subsequently suppress OctreoScan or DOTATATE uptake in the heart.

- Patients with history of neuroendocrine tumors (specially insulinomas)
- Patients taking the medication Octreotide
- Patients on total parenteral nutrition (TPN)
- Women who are pregnant or breastfeeding

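### ROI size is ~20 mm in controls, 15 mm for DOTATATE and unset for OctreoScan foci, so ROI size may contribute to the patient-control difference and to whether a true focus reads 2.0

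*Combined protocol and SAP*

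**What the plan says.** Three measurement rules feed the ratio.

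- **Controls** (I.c Study Rationale, 15 OctreoScan scans from 2013): "Circular region of interests (ROI) of ~20 mm diameter were applied to left ventricular (LV) cavity blood pool", and likewise to the four left ventricular walls. The summary is that "OctreoScan uptake in the heart is indistinguishable from LV blood pool (~ 0.94 ± 0.17").
- **OctreoScan patients** (V.d, Image Interpretation for OctreoScan, item 2): the ratio is formed "using a circular region of interests (ROI) applied to each focus of increased radiotracer uptake". No diameter is given. The background rule, "A background ROI of the same size will be applied to the blood pool in the left ventricular cavity", ties the two circles to each other but sets no number. The one link to the control method is "ROI placement will be confirmed via image fusion with the CT portion from the SPECT/CT study (similar to Figure 2"), which concerns placement. Two physicians do this on both the early and the delayed datasets. Septal, lateral, anterior and inferior wall ROIs are also measured, again with no stated size.
- **DOTATATE patients** (V.d, Image Interpretation for DOTATATE, item 2): "A standardized 15 mm circular region will be placed over each myocardial wall area with the peak activity". "Each ROI will be used to derive maximum (SUVmax) and mean standardized uptake values (SUVmean"), and the plan does not say which of the two forms the ratio that is tested.

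The rules meet in the analysis. Aim 1 asks whether patients "exhibit a myocardial OctreoScan or DOTATATE signal high enough (heart-to-blood pool ratio ≥ 2.0) to be visually detected", for either tracer. Statistical methods compares either tracer with the one control group by an independent t test, and early with delayed OctreoScan ratios by a paired t test.

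**The concern.** The mean ratio inside a circle depends on how much of the circle lies in myocardium. A circle wider than the wall also takes in blood pool and, next to the lung, tissue that reads 0.29 in Table 1. A hot focus then reads lower as the circle grows. If patients and controls are measured with different circles, some of the difference between them may come from the measurement, and a reading of 2.0 stands for a different true ratio at each diameter.

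For OctreoScan the circle is uncontrolled. It may be drawn to the visible focus, or at ~20 mm by a reader who follows the control figure. It may also vary between the two readers and between 4 h and 24 h. The last of these matters because the early-versus-delayed difference is the secondary endpoint, and a change of circle would enter the paired difference directly.

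**Working it through.** **1. The plan's own control figure.** Table 1 gives wall means of 1.02, 1.03, 0.92 and 0.81 with SDs of 0.15, 0.13, 0.15 and 0.15, n = 15.

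- Mean: (1.02 + 1.03 + 0.92 + 0.81)/4 = 0.945.
- Within-wall sum of squares: 14 × (3 × 0.15² + 0.13²) = 1.182.
- Between-wall sum of squares: 15 × (0.075² + 0.085² + 0.025² + 0.135²) = 0.476.
- SD over 60 wall values: √[(1.182 + 0.476)/59] = 0.168.

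This reproduces 0.94 ± 0.17. It is an average over four fixed walls, measured with ~20 mm circles.

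**2. Geometry without blur.** Assumptions: wall w = 10 mm, circle centred on the wall, outside tissue half blood pool and half lung, (1.0 + 0.29)/2 = 0.645. With q = w/D, the share of a circle of diameter D lying in the wall is s = (2/π)[arcsin q + q√(1 − q²)].

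| D | s | Reading of a true 2.0: 2.0s + 0.645(1 − s) |
|---|---|---|
| 10 mm | 1.00 | 2.00 |
| 15 mm | 0.78 | 1.70 |
| 20 mm | 0.61 | 1.47 |

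The gap between 15 and 20 mm is 0.23. This ignores blur and gives every wall a half-lung surround, so it overstates the effect.

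**3. With blur.** A two-dimensional wall lies between blood pool (1.0) and either lung (0.29) or blood-like tissue (1.0). Assumptions not in the documents: wall 8 to 12 mm, blur 6 to 12 mm full width at half maximum, focus length 20 to 40 mm. ROI means, reading at 15 mm minus reading at 20 mm:

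| True ratio | Change |
|---|---|
| 0.94 (normal wall) | −0.01 to +0.04 |
| 2.0 | +0.06 to +0.20 |
| 3.0 | +0.15 to +0.36 |

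- A true 2.0 reads below 2.0 at both diameters (at most about 1.82 at 15 mm). The diameter decides the matter for hotter foci. At a true 3.0, 5 of 12 scenarios read at least 2.0 with 15 mm and below 2.0 with 20 mm; for example 2.07 against 1.86 (wall 12 mm, blur 12 mm, lung outside).
- With the size left open, going from 25 mm to 10 mm raises a true 2.0 by about 0.17 to 0.56.
- If the ratio uses the maximum, the focus numerator does not change with diameter in this noise-free model.

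**4. Scale against the planned test.** The expected difference is 2.0 − 0.94 = 1.06. A shift of 0.06 to 0.20 is 6% to 19% of it. For normal wall, take a pure measurement shift of 0.05 (just above the modelled maximum), SD 0.17 in both groups, 15 controls against 10, 20 or 30 patients, two-sided 0.05. The t test would then be significant in about 11% to 15% of trials, against a nominal 5%.

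**The case against.** A reader might infer that part of any patient-control difference must be ROI size, and that it always favours patients. The documents do not support that.

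- For OctreoScan no size is stated. A reader following the control figure could use ~20 mm, and a large focus could get a larger circle. The direction is unknown.
- A SUVmax ratio depends little on circle size, and the plan derives SUVmax as well as SUVmean.
- In normal wall the effect is close to nil, so circle size cannot produce a gap of 1.0 against 2.0.
- The low anterior (0.81) and lateral (0.92) control values might be taken as evidence of lung dilution. The protocol instead attributes the regional pattern to liver and spleen scatter into the inferior wall and septum. A larger circle on the inferior wall could also take in liver (5.69), which would raise the reading.
- The share of patients reaching 2.0 is not a planned test. The chi-square comparison uses visual grades, which need no ROI; 2.0 is the signal level in the aim and hypothesis.

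These points stand and limit the conclusion. There is also a larger mismatch in normal tissue: patients may be measured at the hottest focus, controls as a four-wall average. Taking the hottest wall in controls would raise 0.945 to about 1.06 to 1.12 (assumed between-wall correlation 0.8 to 0). That is a separate point, and it does not answer this one: different circles still enter one t test, and one of them is undefined.

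**Conclusion.** The point holds as a measurement inconsistency worth correcting, with modest consequences. ROI size may contribute to the patient-control difference in mean-based ratios and to whether a true focus reads 2.0 or more. Its size is about 0.06 to 0.20 at a true 2.0 for 15 against 20 mm, conditional on the assumed wall thickness, blur, focus length and surrounding tissue, none of which the documents give except the lung ratio. For OctreoScan the finding is an uncontrolled measurement of unknown direction, which also reaches the reader comparison and the paired 4 h versus 24 h test.

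Equal diameters would not make the two tracers interchangeable: the protocol itself credits PET with higher contrast and spatial resolution, and no control had a DOTATATE scan.

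**What to change.** - **OctreoScan:** in V.d, set the control diameter (~20 mm) for all patient and blood-pool ROIs, at both time points and for both readers, with the ROI mean as the statistic. The control description does not name its statistic, so confirm that it was also the mean.
- **Alternative:** if the control scans can be retrieved, re-measure all 15 at the diameter used in patients. They were acquired at another institution, so access is not assured.
- **DOTATATE:** state whether SUVmean or SUVmax forms the ratio, and report this tracer separately. Do not carry over the 2.0 or the OctreoScan control comparison as if 15 mm PET ratios were the same measure.

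The cost is a few lines in the image-reading and statistical sections, or 15 re-readings for the alternative. The downside is that a ~20 mm circle dilutes small foci, so patient ratios may read somewhat lower.
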